
Patient-reported Outcome Measures
 
7. To evaluate the effect of TMB-001 0.05% topical ointment on subject QoL during the 12-week treatment period and subsequent 12-week maintenance period.
	
Patient-reported Outcome Endpoints
 
7a. Comparison of proportions of subjects with ≥ 11-point changes from Baseline in IQOL-32 scores at Week 12 between TMB-001 0.05% and vehicle-treated subjects.
 
7b. Comparison of proportion of subjects with reduction from Baseline in DLQI or CDLQI ≥ 4 points at Week 12 between TMB-001 0.05% and vehicle-treated subjects in adult subjects with Baseline scores ≥ 11 and pediatric subjects with Baseline scores of ≥ 13.
 
7c. Comparison of proportion of subjects with ≥ 4-point changes from Baseline in Itch-QoL scores (in subjects with Baseline I-NRS ≥ 7) at Week 24 between subjects randomized to TMB-001 0.05% BID and QD maintenance dosing.
 
7d. Comparison of proportion of subjects with ≥ 4-point changes from Baseline in DLQI or CDLQI at Week 24 between subjects randomized to TMB-001 0.05% BID and QD maintenance dosing in adult subjects with Baseline scores ≥ 11 and pediatric subjects with Baseline scores of ≥ 13.
 
7e. Comparison of proportion of subjects with ≥ 11-point changes from Baseline in IQOL-32 at Week 24 between subjects randomized to TMB-001 0.05% BID and QD maintenance dosing in adult subjects.

Safety Objectives
 
8. To investigate the safety of topically applied TMB-001 0.05% ointment.
 
9. To evaluate incidence of suspected allergic contact dermatitis
	
Safety Endpoints
 
8a. Comparison of proportion of subjects experiencing LSRs through Week 12 between TMB-001 0.05% and vehicle-treated subjects.
 
8b. Comparison of proportion of subjects experiencing TEAEs through Week 12 between TMB-001 0.05% and vehicle-treated subjects.
 
8c. Comparison of proportion of subjects experiencing LSRs through Week 24 between subjects randomized to TMB-001 0.05% BID and QD maintenance dosing.
 
8d. Comparison of proportion of subjects experiencing TEAEs through Week 24.
 
9. Comparison of proportion of subjects demonstrating clinically confirmed allergic contact dermatitis by patch testing through Week 12 between TMB-001 0.05% and vehicle-treated subjects.

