8.3.3 Local Skin Reactions and Evaluation of Allergic Contact Dermatitis

At the time points designated in the SoA ([Table 1](#) and Table 13), the Investigator or designee will evaluate LSRs known to be associated with retinoids (burning/stinging, erythema, erosions, and edema) or other causes regardless of blinded causality assessment within the areas treated with study medication using a 4-point ordinal scale where 0 = none, 1 = mild, 2 = moderate, and 3 = severe.

Note: At Visit 2 (Baseline), the LSR assessment must be performed prior to the application of the study medication.

For drug interruption due to LSRs, refer to structured drug interruption scheme (drug reduction) described in [Section 7.1](#).

Allergic contact dermatitis is defined as a dermatitis that lasts at least 2 weeks, does not begin immediately after drug application (for example, reaction begins after first 24 hours of drug application) and becomes eczematous over time.

If at any point during treatment the Investigator believes that the subject is experiencing an allergic contact dermatitis, the subject should undergo investigator directed patch testing, as defined in [Appendix 11](#).

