Appendix 11: Patch Testing

Contact dermatitis represents two forms of exogenous eczematous dermatitis; irritant and allergic contact dermatitis. Irritant dermatitis represents a direct toxic effect of chemicals on epidermal cells resulting in destruction of skin cells and impairment of barrier function. Allergic contact dermatitis is delayed type hypersensitivity (allergy) to small molecular weight molecules and requires initial sensitization and then subsequent elicitation. Allergic contact dermatitis most often occurs within days to weeks after repeated exposure to provocative chemicals. Allergic contact dermatitis to active ingredients and excipients of topical products is well described in the literature.

Patients suspected of having an adverse event of hypersensitivity/allergic contact dermatitis to the topically applied investigational product will be evaluated by the investigator by patch testing. If temporary withdrawal of the investigational medication does not result in amelioration of symptoms, topical corticosteroids may be employed and the patient can discontinue the trial. The presumption of possible allergic contact dermatitis will be based on the investigator's evaluation of an eczematous appearing eruption (erythematous, scaly, vesicular, or eroded patch or plaque) occurring at a previously clear site that is the recent or current recipient of the investigational product.

Patch test application sites should ideally be clinically inactive without any eczematous dermatitis, and as inactive an area of ichthyosis as is clinically practicable. The site of the patch test should not be adjacent to the currently suspected eczematous area. Patients utilizing topical corticosteroids for other local skin reactions should washout for 1 week prior to the initiation of patch testing. Flat areas such as the upper back are preferred, but alternative sites such as the ventral forearm or thigh can be used if the back is not clear. Hair bearing areas should be prepped with a safety razor to ensure adhesion of the test material.

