Patch test consents and disposition of signs and symptoms will be recorded in the source document and eCRF. The investigator will apply an approximately 5 mm ribbon of investigational topical medication from the patient's existing medication supply to the interior portion of an IQ ultra patch test chamber (Chemotechnique, Sweden) and secured with additional paper tape. Two additional tests will consist of a vehicle control and white petrolatum that will be supplied by the sponsor upon request. The chambers will remain in place for approximately 48 hours (2 days). Patients will present to the clinical site for removal of the patch test and initial interpretation by the investigator. (See interpretation guideline below from the International Contact Dermatitis Research Group). Patients will return 1-4 days after removal for an additional and final interpretation of the patch test. Patch test results will be recorded in the source document and eCRF.

Patch test interpretation according to the International Contact Dermatitis Research Group (ICDRG)

- ?+ Doubtful
- + Mild reaction, possible erythema, infiltration and papules
- ++ Strong reaction, erythema, infiltration, papules and vesicles
- +++ Very strong reaction, intense erythema, infiltration and coalescing vesicles
- IR** Irritant reaction, of various types

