1.4.5 Safety Parameters

The safety endpoints include the following:

- Comparison of proportion of subjects experiencing local skin reactions (LSRs) through Week 12 between TMB-001 0.05% and vehicle-treated subjects.
- Comparison of proportion of subjects experiencing treatment-emergent adverse events (TEAEs) through Week 12 between TMB-001 0.05% and vehicle-treated subjects.
- Comparison of proportion of subjects experiencing LSRs through Week 24 between subjects randomized to TMB-001 0.05% BID and QD maintenance dosing.
- Comparison of proportion of subjects experiencing TEAEs through Week 24.
- Comparison of proportion of subjects demonstrating clinically confirmed allergic contact dermatitis by patch testing through Week 12 between TMB-001 0.05% and vehicle-treated subjects.

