7.2.1 Local Skin Reactions

The incidences of local skin reactions (LSRs) will be summarized for all visits according to the skin irritation scale (Grade 0 – none, Grade 1 – mild, Grade 2 – moderate, Grade 3 – severe) and type of reaction (burning/stinging, erythema, erosions, and edema). Changes from baseline will also be summarized for all visits and will be categorized into

'worsened' and 'same or improved' categories. For subjects reporting more than one occurrence of the same type of reaction, the most severe reaction will be used for the summary.

The proportion of subjects experiencing a LSR through Week 12 will be reported along with exact binomial 95% confidence intervals, using the primary safety data presentation. The proportion of subjects experiencing a LSR through Week 24 will be reported along with exact binomial 95% confidence intervals, using the open-label dosing data presentation. Additionally, the Week 12 analysis will be repeated, separating subjects that had ≥ 10 Cetaphil applications within the first 21 days, versus subjects that had < 10 Cetaphil applications.

Additionally, the number and percentage of subjects who had suspected allergic contact dermatitis will be provided for all visits, along with exact binomial 95% confidence intervals. The number of subjects with confirmed cases of allergic contact dermatitis will be reported as well; subjects with confirmed cases are defined as those who had a suspected event reported, **and** allergic contact dermatitis reported as an AE.

A by-subject listing will be provided for all local skin reaction data.

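### SAP 7.2.1 counts allergic contact dermatitis as confirmed on suspicion plus an adverse event entry, whereas the stated safety endpoint rests on the patch test

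*SAP*

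**What the plan says.** Protocol Table 2, safety endpoint 9, compares the proportion of subjects with "clinically confirmed allergic contact dermatitis by patch testing through Week 12 between TMB-001 0.05% and vehicle-treated subjects". The synopsis carries the same endpoint, and SAP 1.4.5 repeats it: "Comparison of proportion of subjects demonstrating clinically confirmed allergic contact dermatitis by patch testing through Week 12".

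The analysis is described only in SAP 7.2.1. There, "subjects with confirmed cases are defined as those who had a suspected event reported", and the sentence goes on to require that allergic contact dermatitis was also reported as an adverse event. No patch-test result is mentioned. Suspected cases get a number, a percentage and an exact binomial 95% confidence interval for all visits. Confirmed cases get a number, with no time window stated. The preceding paragraph of the same section does state a window for local skin reactions: "The proportion of subjects experiencing a LSR through Week 12 will be reported along with exact binomial 95% confidence intervals".

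On the clinical side, protocol 8.3.3 says that when the investigator believes allergic contact dermatitis is present, "the subject should undergo investigator directed patch testing". Appendix 11 describes the test, its graded readings and a final interpretation, and states: "Patch test results will be recorded in the source document and eCRF".

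**The concern.** Endpoint 9 and the table that is meant to report it use the same word, confirmed, for two different things. The endpoint means confirmed by a test. The SAP rule means suspected by the investigator and entered as an adverse event under that name. Appendix 11 exists to separate allergic from irritant dermatitis and gives irritant reactions their own reading. Protocol 7.1 expects transient skin irritation with topical retinoids and notes that the vehicle may also cause local reactions. A count that ignores the test does not use the information collected to make that distinction.

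If 7.2.1 is programmed as written, no summary table reports endpoint 9 as defined, and a reader of the study report would take the row labelled confirmed to be patch-test confirmed. The missing window is a lesser part of the same problem: a count without a stated cut-off is not clearly the Week 12 comparison that SAP 1.4.5 names.

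**Working it through.** No arithmetic applies. The check sets the passages side by side.

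**Step 1. Does the adverse event entry imply a positive test?** Three places could make the link, and none does.
- Protocol 8.3.3 defines allergic contact dermatitis clinically, by its duration, delayed onset and eczematous course. The definition does not refer to a test.
- Appendix 11 opens the testing procedure with "Patients suspected of having an adverse event of hypersensitivity/allergic contact dermatitis". The test is the evaluation of an event already under suspicion. The text does not say that the adverse event is entered only after a positive reading.
- Appendix 3 asks that the diagnosis be recorded as the adverse event where possible and that new information be entered in the eCRF. It does not tie this diagnosis to a patch-test reading.

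**Step 2. Can a suspected case be without a test result?** Protocol 8.3.3 words testing as something that should happen, while Appendix 11 says patients will be tested. Appendix 11 also says "Patch test consents and disposition of signs and symptoms will be recorded in the source document and eCRF", which suggests a separate consent, and it allows the patient to leave the trial. Suspected cases without a result are therefore foreseeable, although the documents give no rate.

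**Step 3. Apply both definitions to the possible cases.** All rows are suspected cases.

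| Adverse event term | Final patch test | Endpoint 9 / SAP 1.4.5 | SAP 7.2.1 |
|---|---|---|---|
| Allergic contact dermatitis | Positive | Confirmed | Confirmed |
| Allergic contact dermatitis | Negative, doubtful or irritant | Not confirmed | Confirmed |
| Allergic contact dermatitis | None | Not confirmed | Confirmed |
| Another term | Positive | Confirmed | Not confirmed |
| Another term or none | Negative or none | Not confirmed | Not confirmed |

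The two definitions disagree in three of the five rows, and in both directions. The second row treats a doubtful or irritant reading as not confirming, which is the ordinary meaning. Neither document says which readings count as positive.

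**Step 4. The window.** SAP 1.4.5 states Week 12 for this parameter. SAP 7.2.1 does not repeat it for confirmed cases. The rule in SAP 7.2 that assigns events by the period in which they began is written for treatment-emergent adverse events and for the analyses listed before it in that section. It is not expressly carried into 7.2.1.

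**Step 5. Is the change declared?** SAP 1.2 says that the SAP outlines its differences from the protocol. Section 8 lists two, the move of VIIS-50 and the switch to WI-NRS. The addendum does not touch allergic contact dermatitis. SAP 1.2 also says that the SAP supersedes the protocol's analysis plan, but this does not settle the matter, because 1.4.5 and 7.2.1 are both in the SAP.

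**Step 6. Size.** A size would need the number of suspected cases, the share tested, the share positive and the adverse event terms used. The documents give none of these.

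**The case against.** The strongest defence is that 7.2.1 requires two things. If the adverse event entry meant no more than suspicion, the second condition would add nothing. It is reasonable to read it as the investigator's diagnosis after the testing that 8.3.3 and Appendix 11 prescribe, kept current under the recording rules of Appendix 3. This may well be what was intended. It stands as a possible intention but not as a rule: the link to the test is written nowhere, and a programmer following 7.2.1 would not look at the patch-test data.

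A second defence is that the stakes are low. The safety objective in SAP 1.2.5 is the incidence of suspected cases, supplemented by confirmatory testing, and suspected cases are fully summarised. SAP 3.2.1 lists all eCRF data by subject and gives percentages for categorical variables, so a reviewer could partly rebuild the endpoint, and the absence of the word percentage in 7.2.1 is not itself a gap. This stands, and it limits the weight of the point.

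Two stronger readings are tempting, and the documents do not support either.
- A reader might infer that the error will mostly inflate the count. The recording rules in Appendix 3 cut both ways: they make it likelier that a patch-positive case carries the right term, and equally that a case with a negative test is re-termed. The direction is not established.
- A reader might infer that, because vehicle subjects with less than a 1-point IGA reduction can cross to open-label TMB-001 at Week 12, their later cases will be counted under vehicle. SAP 3.11.3 does define the primary safety columns by initial randomization. It also provides a separate open-label presentation for Period 3, with its own column for subjects who had vehicle in the blinded phase, and SAP 1.4.5 states the Week 12 window. The fair criticism is only that 7.2.1 does not say which presentation and window apply to confirmed cases. The number of subjects who might cross over measures no misclassification.

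**Conclusion.** The definition in SAP 7.2.1 yields a different quantity from the endpoint stated in the protocol and in SAP 1.4.5, and the difference is undeclared. It should be corrected. The two counts can differ in either direction, by an amount that the documents do not allow anyone to derive. The unstated window is a secondary gap in wording, largely covered by SAP 1.4.5 and 3.11.3 once 7.2.1 refers to them.

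The conclusion rests on the text alone: no passage in either document makes the adverse event entry conditional on a positive patch test. It would fall if eCRF completion instructions outside these documents imposed that condition. Even then, 7.2.1 should say so. No alpha, power or efficacy conclusion is affected.

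**What to change.** In SAP 7.2.1, derive confirmed status from the final patch-test interpretation recorded in the eCRF, with the readings that count as positive fixed before unblinding and with clinical input. Report the number and percentage by initial arm through Week 12. An exact 95% confidence interval, as already planned for suspected cases, is optional. Show suspected cases without a test result in their own row. Put Period 3 cases in the open-label presentation of SAP 3.11.3. State which date places a case in the window: with about 2 days of wear and a final reading 1 to 4 days after removal, the result comes 3 to 6 days after application (2 + 1 to 2 + 4). Keep the suspected-plus-adverse-event count only under a label that says what it is. Record the change in SAP section 8, or in the clinical study report if the SAP is already final, as SAP 1.2 provides.

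The cost is a few lines of SAP wording and one revised table. By Appendix 11 no new data are needed, although the eCRF itself was not available to check that the result sits in a usable field. Some suspected cases may have no result; the separate row makes that visible but does not resolve it.

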7.2.2 Adverse Events and LSRs in the Maximal Use Arm

Adverse events and local skin reactions in subjects from the maximal use arm will be listed separately in a by-subject data listing. Event types will be provided to distinguish between study drug application site AEs and other AEs.

7.3 Clinical Laboratory Data

Clinical laboratory data will be expressed in international system of units (SI).

The actual value and change (both actual and percent) from baseline to each on-study evaluation will be summarized using descriptive statistics using the primary safety data presentation for each clinical laboratory parameter, including hematology, clinical chemistry, and qualitative urinalysis. Measurements that are unscheduled and that do not fall in a protocol-specified visit window will not contribute to the summary tabulations.

Laboratory tests will be classified in comparison to their reference range as: LN (Low Normal), LP (Low Panic), N (Normal), HN (High Normal), HP (High Panic), AB (Abnormal), SC (See Comment), and Blank when not used. Using these classifications, a shift table will be created to present any change from baseline in reference ranges in all laboratory tests across all post-baseline visits, including the worst post-baseline visit. Percentage of subjects will be calculated using the number of subjects with a baseline value and a non-missing value at the specified post-baseline visit as the denominator.

All laboratory data, including serology results, will be provided in by-subject data listings. A listing of all abnormal clinical laboratory results will be provided as well.

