Under all circumstances when emollients are mandated by protocol or required for treatment of LSRs, emollients should be applied either 3-5 hours prior to or following application of TMB-001 0.05% or Vehicle as applicable. Emollients under all circumstances should be withheld for 24 hours prior to any scheduled efficacy visits as outlined in the SoA (Table 1 and Table 13).

Study treatment details are provided in Table 6. The vehicle ointment contains only the inactive ingredients and color additive so that the active and vehicle formulations are indistinguishable.

Table 6 Study Treatments

Study Treatment Name:	TMB-001 0.05%	Vehicle
Dosage Formulation:	Ointment	Ointment
Unit Dose Strength(s)/Dosage Level(s):	0.05%	Not applicable
Route of Administration	Topical	Topical
Dosing Instructions:	Once a day (QD) for first 3 weeks then twice a day (BID) (morning and evening) for next 9 weeks, then QD or BID for 12 weeks (depending on randomization)	QD for first 3 weeks then BID (morning and evening) for next 9 weeks

Study Treatment Name:	TMB-001 0.05%	Vehicle
Packaging and Labeling	Study medication will be provided in aluminum tubes. Each aluminum tube will be labeled as required per country requirement.	Vehicle ointment will be provided in aluminum tubes. Each aluminum tube will be labeled as required per country requirement.
Storage Temperature	Store at 36°F to 46°F (2°C to 8°C) until assigned to study participant. Once assigned, store at 68°F to 77°F (20°C to 25°C), excursions permitted to 59°F to 86°F (15°C to 30°C).	Store at 36°F to 46°F (2°C to 8°C) until assigned to study participant. Once assigned, store at 68°F to 77°F (20°C to 25°C), excursions permitted to 59°F to 86°F (15°C to 30°C).
Manufacturer	[REDACTED] [REDACTED], USA	[REDACTED], USA

Note: Subjects in both the TMB-001 0.05% treatment and the vehicle treatment group will apply a bland emollient (Cetaphil™ Moisturizing Lotion) provided by the Sponsor during Study Period 1 (see [Section 4.1](#)).

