1.3.1 Overview of Study Design

The study consists of three periods:

- **Period 1 – Induction (3 weeks):**

At the beginning of the 3-week induction period, eligible subjects will be randomized (2:1 ratio) to either TMB-001 0.05% once-a-day (QD) or Vehicle QD treatment, with use of mandatory standardized bland emollient (Cetaphil™) provided by the Sponsor.

- **Period 2 – Treatment (9 weeks):**

The dosing frequency in the 9-week treatment period will be increased in each treatment group to TMB-001 0.05% or Vehicle twice a day (BID). Mandatory bland emollient will be discontinued.

- **Period 3 – Maintenance (12 weeks):**

At Week 12, eligible subjects in the TMB-001 treatment group will be randomized (1:1 ratio) to open-label treatment with TMB-001 0.05% BID or QD. To be eligible, subjects must have achieved a \geq 1-point reduction in IGA score from Baseline.

Subjects with $<$ 1-point reduction in IGA score from Baseline will be discontinued from the study.

Vehicle-treated subjects who achieved $<$ 1-point reduction in IGA score from Baseline are eligible to cross over to the TMB-001 0.05% BID treatment group. Subjects with a \geq 1-point reduction in IGA score from Baseline will be discontinued from the study.

Subjects at the end of the study or subjects discontinued from the study at any time will be followed-up for an additional 2 weeks for the monitoring of adverse events.

Optional Maximal Use Arm

Adult and pediatric subjects, at a subset of preselected centers, will be enrolled in an open-label Optional Maximal Use arm to evaluate the systemic exposure and safety of topical TMB-001 0.05% ointment for the treatment of CI under maximal use conditions. Initially, adult CI subjects (\geq 17 years; n=16) and pediatric subjects (12-16 years; n=7-9) will be dosed for 14 days with TMB-001 0.05% BID. Following an interim PK analysis and based on the exposure data for subjects aged \geq 12 years, pediatric subjects aged 6 to 11 years (n=7-9) will begin dosing with TMB-001 0.05% BID for 14 days. Following the 14-day PK assessment period, subjects will receive TMB-001 0.05% BID treatment for 10 additional weeks to provide additional safety and limited efficacy data.

The schedule of assessments for both the Phase 3 study and the optional maximal use arm can be found in the study protocol.

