3.11.3 Safety

The primary data presentation for all safety analyses (henceforth referred to as 'primary safety data presentation') will have the following table header:

TMB-001 0.05% (N=xx)	Vehicle (N=xx)	Overall (N=xx)
----------------------------	-------------------	-------------------

The TMB-001 0.05% and Vehicle columns will represent the subjects initially randomized to either TMB-001 0.05% or vehicle, regardless of the second randomization allocation in Period 3.

Additionally, a data presentation specific to Period 3 will be used:

	OL TMB-001 0.05% BID (N=xx)			
OL TMB-001 0.05% QD (N=xx)	TMB-001 0.05% in	Vehicle in Blinded	Total OL TMB- 001 0.05% BID (N=xx)	Overall (N=xx)

	Blinded Phase (N=xx)	Phase (N=xx)		
--	-------------------------	-----------------	--	--

This data presentation (henceforth referred to as 'open-label dosing safety data presentation') will be used for all analyses of safety endpoints specifically during Period 3, comparing TMB-001 0.05% BID and QD maintenance dosing.

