7.0 SAFETY ANALYSIS

All analyses in this section will be performed using the Safety Population and presented as described in Section 3.11.3, unless otherwise indicated.

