7.4 Vital Signs

Vital sign parameters will include temperature, systolic and diastolic blood pressure, heart rate, and respiration rate. The actual value and change from baseline to each on-study evaluation will be summarized using descriptive statistics using the primary safety data presentation for each vital sign parameter. Measurements that are unscheduled and that do not fall in a protocol-specified visit window will not contribute to the summary tabulations.

Vital sign measurements and changes from baseline will be presented for each subject a data listing.

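### The worst-post-baseline lab shift row (SAP 7.3) can mix vehicle and TMB-001 exposure under 'Vehicle', because labs and vital signs are not split at the Week 12 crossover

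*SAP*

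**What the plan says.** **Layout for labs and vital signs.** SAP 7.3 has lab values and changes at each on-study evaluation "summarized using descriptive statistics using the primary safety data presentation for each clinical laboratory parameter". SAP 7.4 treats vital signs likewise, "using the primary safety data presentation for each vital sign parameter".

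**Columns.** SAP 3.11.3 defines them: "The TMB-001 0.05% and Vehicle columns will represent the subjects initially randomized to either TMB-001 0.05% or vehicle".

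**Shift table.** SAP 7.3 adds a reference-range shift table for all laboratory tests "across all post-baseline visits, including the worst post-baseline visit". That sentence names neither a layout nor a period. The layout comes from elsewhere. SAP 7.0 states "All analyses in this section will be performed using the Safety Population and presented as described in Section 3.11.3, unless otherwise indicated", and 3.11.3 calls the initial-arm layout "The primary data presentation for all safety analyses".

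**Treatment after Week 12.** Protocol Table 6 gives vehicle dosing as "QD for first 3 weeks then BID (morning and evening) for next 9 weeks", with nothing after that. Under SAP 1.3.1, vehicle subjects with less than a 1-point IGA reduction are "eligible to cross over to the TMB-001 0.05% BID treatment group"; the other vehicle subjects are discontinued.

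The SAP addendum does not alter 7.3 or 7.4.

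**The concern.** A column headed Vehicle in a comparative safety table will be read as control data. From Period 3 onward, its scheduled entries come from people assigned to the active ointment.

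In a by-visit table the visit label gives this away. A worst-value row carries no visit label: it reduces each subject to one value, and for a crossover that value may come from either treatment. The comparison at stake is the lab shift between drug and vehicle. Labs matter here because Protocol 2.3 lists renal or hepatotoxicity among the notable reactions to oral isotretinoin, and Protocol Table 17 schedules fasting lipids at Weeks 12 and 24. The protocol also expects low systemic exposure from the ointment, so no safety signal is being suggested.

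**Working it through.** The plan states no figure on this point, so the check is mainly a comparison of passages.

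**1. Who is in the Vehicle column after Week 12?** Vehicle subjects with a reduction of 1 point or more leave, with Visit 6 as their end-of-study visit (Protocol Table 1, footnote c). The rest may cross over to TMB-001 BID. No one is assigned vehicle in Period 3.

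**2. Which scheduled visits are affected?**
- Labs: Visits 6 and 9 are the post-baseline draws (Protocol Table 1 and 10.3.1.3.3). Visit 9 falls in Period 3, so 1 of 2.
- Vital signs: Visits 4, 5 and 6 precede Period 3. Visit 7 and end of study follow, so 2 of 5. The last mark in the Table 1 row appears under Visit 10 in the text as extracted, but Protocol 10.3.1.3.1 summarizes through Visit 9. Visit 7 alone is enough for the point.

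**3. Is the period split handled elsewhere?**

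| Output | Layout | Period rule |
|---|---|---|
| TEAEs (SAP 7.2) | both | counted only in the period of onset |
| LSR proportions (SAP 7.2.1) | primary through Week 12; open-label through Week 24 | separate time points |
| Labs by visit (7.3), vital signs (7.4) | primary | none |
| Lab worst-value shift (7.3) | primary, by default from 7.0 and 3.11.3 | none |

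SAP 2.3 also has the Safety population analyzed by treatment actually received. A Vehicle heading over Period 3 values conflicts with that rule.

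**4. What does the worst-value row contain?** For a crossover it is the worse of a vehicle-period value and a TMB-001-period value. Who contributes a second scheduled draw depends on response, in opposite ways: vehicle subjects continue with less than a 1-point reduction, TMB-001 subjects with at least 1 point. No direction of bias can therefore be stated.

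**5. Can the size be found?** Only the planned arm size is available: 110/3 = 36.7 vehicle subjects.
- Crossovers, assuming that 10% to 70% of vehicle subjects have at least a 1-point reduction: 36.7 × 0.90 = 33 down to 36.7 × 0.30 = 11. With an assumed 15% loss before Week 12, 36.7 × 0.85 = 31.2, giving 31.2 × 0.90 = 28 down to 31.2 × 0.30 = 9.
- Extra abnormal subjects in the Vehicle worst-value row, with no drug effect: 31.2 × c × p × (1 − p) × (1 − φ). Here c is the crossover fraction, p the abnormality rate in each period and φ the within-subject correlation.
  - c = 0.9, p = 10%, φ = 0: 31.2 × 0.9 × 0.10 × 0.90 = 2.5.
  - c = 0.3, p = 2%, φ = 0: 31.2 × 0.3 × 0.02 × 0.98 = 0.2.
  - φ = 1: 0.
- As a share of abnormal entries in that row, x/(1 + x) with x = c(1 − p)(1 − φ): c = 0.9, p = 2%, φ = 0 gives 0.882/1.882 = 47%; φ = 1 gives 0%.

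All values of c, p and φ are assumptions. A range that includes zero shows only that the documents do not settle the size.

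**The case against.** **The columns are openly defined by initial arm.** SAP 3.11.3 says so and adds that the second allocation is disregarded. This answers the by-visit complaint in part: the rows carry visits, and a reader who knows the design can decode them. It does not cover crossover, because only TMB-001 subjects are re-randomized (SAP 1.3.2). Vehicle crossovers simply go to BID.

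**The mixture can be recovered by subtraction.** With two scheduled draws, each with its own shift row, the worst-value count minus the Week 12 count is roughly the number abnormal only at Visit 9 or early termination. This stands as an approximation. The remainder still pools early-termination vehicle values with crossover values, and the reader should not have to do it.

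**Important abnormalities are separated anyway.** Protocol Appendices 2 and 3 make clinically significant lab abnormalities AEs, and SAP 7.2 splits TEAEs by period. By-subject listings are also planned. This stands and limits the harm.

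**Stronger readings that the documents do not support.**
- A reader might infer that the shift table has no layout at all. SAP 7.0 with 3.11.3 supplies one.
- A reader might infer that every Visit 9 value under Vehicle is a TMB-001 value. Visit 9 is also the early-termination visit, and SAP 3.10 tabulates by the visit recorded on the eCRF. A vehicle subject who stopped before Week 12 may appear there with genuine vehicle data.
- A reader might take the 47% above as an estimate. It is one corner of an assumed range that reaches zero.

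**Conclusion.** The point holds as a minor one. Followed as written, SAP 7.3 produces a Vehicle worst-post-baseline shift row that can combine vehicle and TMB-001 exposure within a subject, so it is not a drug-versus-vehicle comparison. By-visit Period 3 rows for labs and vital signs are mislabelled but recognisable.

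Placing the shift table in the primary presentation relies on the default in SAP 7.0 and 3.11.3, since its own sentence names no layout. The tables are descriptive: no hypothesis test, endpoint or Week 12 row, including the Week 12 shift row, is affected. The numerical effect cannot be estimated from the documents, and no direction is claimed.

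**What to change.** In SAP 7.3 and 7.4, limit the Vehicle and TMB-001 columns of the primary safety presentation, including the worst-post-baseline shift row, to assessments in Periods 1 and 2. Define this as:
- assessments through Visit 6 (Week 12), counting Visit 6 assessments made on the day of, but before, the first open-label application; and
- early-termination assessments of subjects who never started Period 3.

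The same-day rule is needed because SAP 7.1 defines the first open-label dose by date only. A strict date cut could drop Week 12 labs drawn on the day that open-label treatment starts.

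Present Period 3 labs and vital signs in the existing open-label safety presentation, which already separates former vehicle subjects. Name the shift table's layout. Extend the scope sentence in 3.11.3, which now ties that presentation to safety endpoints; the endpoints in SAP 1.4.5 do not include labs or vital signs.

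**Cost.** SAP wording and a table filter. The pooled 24-week summary of the initial TMB-001 arm leaves the comparative table, and the open-label layout splits that arm into QD and BID. The pooled summary can be kept as a separate, non-comparative table. With one scheduled lab draw in Period 3, a worst-value row for that period would nearly repeat Visit 9 and could be omitted.
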